## 2.4.3. CLN-PRO-V002 Study Results (24 M)

Recruitment began in October 2013 and was completed in June 2014 with 20 patients implanted. Thirteen patients completed the 2 year follow up visit. Of the seven patients terminating the study early, three died and four were withdrawn after occlusion of the HAV. None of the deaths were considered related to the investigational device or procedure.

Kaplan-Meier analyses in which deaths were censored revealed primary, primary assisted, and secondary patency probability rates of 79.2%, 79.0%, and 89.5% at Week 26, 63.3%, 63.2%, and 84.2% at Month 12, 63.3%, 63.2%, and 79.0% at Month 18, and 58.1%, 57.9%, and 73.7% at Month 24.

Six patients (30%) required at least 1 graft intervention to maintain or restore HAV patency during the study. Four patients required 1 intervention and 1 patient each required 3 and 4 interventions. Most interventions successfully restored patency. However, in 1 patient the graft patency could not be restored and the HAV was replaced with an alternative bypass graft. Two patients, who had previously undergone successful interventions, developed a recurrent thrombosis which was not treated and the HAV was left occluded. Two patients experienced HAV thrombosis with no or minimal symptoms and refused interventions on the HAV.

Confidential

All 20 patients experienced AEs (a total of 92 events). Thirty-one of these events in 13 patients were considered serious. The most frequent AEs reported included graft thrombosis (35% of patients), anastomotic stenosis (20% of patients), lymphocele (20% of patients), and local swelling (15% of patient). Those serious adverse events (SAEs) reported by at least 2 patients were graft thrombosis (6 patients, 30%) and anastomotic stenosis (2 patients, 10%).

No patient showed an increase in PRA levels. Two patients had a significant (>2-fold) increase from baseline in IgG levels. One of these patients experienced a thrombosis of the HAV between 3 and 6 months after implantation, while the other patient has had no HAV-related AEs and continues to have primary patency. Neither patient has had any evidence of dilatation or structural degeneration of the HAV.

#### CLN-PRO-V002 Conclusions:

- Humacyte HAV was safe and well tolerated in PAD patients.
- The HAV is able to withstand long term use in a high pressure, high outflow resistance arterial circuit.
- Patency rates for the HAV are within the ranges of patency rates of synthetic and autologous grafts presented in the literature.
- Humacyte HAV was not immunogenic.

#### 2.4.4. Experience in Hemodialysis Patients

Two Phase 2 trials, one in Poland (CLN-PRO-V001) and one in the US (CLN-PRO-V003) have completed enrollment. Both recruited subjects requiring hemodialysis access for ESRD whom were not suitable for creation of an autologous arteriovenous fistula (AVF). Most subjects had undergone previous vascular access procedures, in many cases multiple attempts including both AVFs and synthetic grafts. Initial results from these Phase 2 studies are discussed below.

The primary objectives of these two studies are to evaluate both the safety of HAV and its efficacy in terms of primary and secondary patency at 6 months. Secondary objectives include measurement of a PRA response, development of IgG antibodies to the ECM material in the HAV and a 2-year evaluation of patency and an assessment of the need for interventions to maintain/restore patency. Follow up has now been extended up to 120 months.

A Phase 3 randomized study comparing HAV with expanded PTFE (ePTFE) grafts (CLN-PRO-V006) has completed enrollment in the US, Europe, and Israel. Preliminary Month 18 results are presented below. A second Phase 3 randomized study (CLN-PRO-V007) comparing HAV with

Confidential

AVF is currently enrolling in the US. As the sponsor is blinded, no efficacy information currently available for CLN-PRO-V007; however, blinded safety data is presented in the IB. A Phase 2 study of ESRD patients in Poland (CLN-PRO-V011) has primary assessments ongoing, and no safety or efficacy information is currently available.

## 2.4.5. CLN-PRO-V001 and CLN-PRO-V003 Study Results (24 M)

All subjects (n=60) have now completed at least 24 months since implantation (or had a censoring event). The first subjects recruited are now beyond 60 months after HAV implantation, some with functioning HAV for hemodialysis access. Together these two trials provide more than 150 years of follow up during which the HAV has been used for more than 15,000 hemodialysis sessions.

When HAV thrombosis has occurred, it has almost always been managed successfully, often allowing immediate resumption of dialysis without the need for the placement of a dialysis catheter. One non-serious arteriovenous (AV) graft aneurysm was reported in Study CLN-PRO-V001 (moderate in intensity, considered possibly related to the investigational medicinal product [IMP] and considered not related to procedure – this patient died before the Sponsor could complete the follow up of this event). An expected number of small pseudoaneurysms have been observed, which is consistent with all surgically-created hemodialysis access. Most have resolved spontaneously with only 2 cases requiring surgical intervention. Flow rates through the HAV were more than sufficient to allow for effective dialysis.

In both studies, the product has generally been well tolerated and blood chemistry, hematology and coagulation data are not indicative of any HAV-associated toxicity. Immunogenic response to the HAV material has not been observed as demonstrated by a general lack of HAV-related change in PRA levels (Class I or II). Three subjects had elevations in their PRA levels: all 3 subjects had experienced one or more renal transplant failures; one subject recently; one subject developed septic shock about a month before the elevated value; and the third subject, who was severely debilitated with a decubitus ulcer, died approximately a month after HAV abandonment.

IgG titers increased in 5 subjects; in 4 cases, the IgG titer increased and then decreased while the HAV remained functional with no clinical evidence of an inflammatory response; in one case the IgG titer increase occurred in a subject who maintained primary patency. AEs related to the HAV / access site (excluding thrombotic events) were few; there have been only three access-site infections, of which only one required removal of part of the HAV. There have been:

- 1 transplant (known to be functioning well at 12 months post-transplant)
- 15 deaths, all after abandonment or during follow-up; none of the deaths were considered related to the presence of the HAV

Patency data for the two studies in dialysis access has been pooled for a combined Kaplan Meier analysis (Lawson, 2016). Based on these Kaplan-Meier plots, the patency at 6, 12 and 24 months is estimated to be 60%, 26% and 15% (primary patency) and 97%, 89% and 77% (secondary patency).

## 2.4.6. CLN-PRO-V006 Preliminary Study Results (18 M)

Details of Study CLN-PRO-V006 can be found in the IB. The CLN-PRO-V006 study was designed to enroll a broad range of ESRD patients in whom a clinical decision has been made to implant a 'graft' to provide vascular access for hemodialysis. The trial was limited to adults (≥18 years old), and subjects were either on hemodialysis or expected to start dialysis within 12 weeks of conduit implantation. The standard synthetic graft implanted in this clinical setting is an ePTFE graft (6 mm by 40 mm, straight, standard wall, non-stretch, and non-tapered).

The primary objective of the study is to compare the secondary patency of the HAV with that of the ePTFE graft when used as a conduit for hemodialysis. Key secondary objectives of the study are to compare the primary patency of the HAV with that of the ePTFE graft (efficacy) and to compare the rate of access-related infections for the HAV with that of the ePTFE graft (safety).

A summary of losses of secondary patency (events) for ePTFE and HAV are shown in Table 2. At 6 and 12 months post-implantation, the HAV arm had 9 and 6 fewer losses, respectively, of secondary patency than the ePTFE arm. At 18 months, the ePTFE arm had 4 fewer losses of secondary patency than the HAV arm.

Time Point	Number of ePTFE Patency Losses	ePTFE Kaplan-Meier Probability of Patency	Number of HAV Patency Losses	HAV Kaplan-Meier Probability of Patency
6 Months	21	88.0%	13	92.3%
12 Months	33	80.7%	29	81.8%
18 Months	37	77.6%	41	73.0%

 Table 2
 Summary of Secondary Patency Losses - ITT Set

ePTFE=expanded polytetrafluoroethylene; HAV=Human Acellular Vessel; ITT=Intent to Treat

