#### Confidential

The CLN-PRO-V006 Statistical Analysis Plan pre-specified the use of the Cox Proportional Hazards model to compare the secondary patency rates of HAV and ePTFE. The observed hazard ratio for loss of secondary patency at 18 months is 1.19, with lower and upper 95% confidence interval (CI) of 0.78 and 1.81, respectively. Since the observed upper 95% CI is greater than the non-inferiority margin, we failed to reject the null hypothesis, and therefore, could not establish non-inferiority of HAV relative to ePTFE.

However, given that the hazards for loss of secondary patency between HAV and ePTFE were not proportional (i.e., the curves for secondary patency cross near 400 days, making the relative risks of loss of patency non-proportional over time), the pre-specified Cox Proportional Hazards model is not ideally suited to analysis of the CLN-PRO-V006 secondary patency data. Therefore, a sensitivity analysis was performed using the non-parametric restricted mean survival time (RMST) method, which does not make assumptions regarding proportionality of hazards between the two arms of the trial. RMST estimates a gain or loss in the event-free survival time due to treatment versus control in a specified time period. The results from the RMST analysis indicated that the time to failure of secondary patency was delayed, on average, by 11 days in the HAV arm compared to the ePTFE arm at the 18 month time point, and non-inferiority of the HAV in comparison to ePTFE was demonstrated with this alternative RMST analysis.

The time to loss of primary patency was significantly shorter for the HAV than for ePTFE, with a hazard ratio of 1.89. Since losses of primary patency for the HAV seemed to briefly accelerate around 60 to 90 days, it is unclear the extent to which study-mandated ultrasounds at 60 and 90 days, combined with the lack of experience in managing the HAV at most study sites, may have triggered interventions on the HAV study conduit that would have led to a loss of primary patency at those times.

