1.4 Objectives

1.4.1 Primary Objectives:

This is an open label Phase 2 study. There is no formal hypothesis testing.

Statistical Analysis Plan	
CLN-PRO-004	

Final Analysis 8/23

Safety:

• To evaluate the safety and tolerability of the Humacyte HAV in PAD patients undergoing femoro-popliteal bypass surgery

Efficacy:

- To determine the patency (primary, primary assisted and secondary) rate of the Humacyte HAV at Month 12
- To determine the incidence of hemodynamically significant stenosis (>70%) defined by duplex ultrasound, and the time to stenosis development

1.4.2 Secondary Objectives:

Safety:

- To assess changes in the panel reactive antibodies (PRA) response after HAV implantation
- To determine mechanical stability of the HAV based on freedom from aneurysmal degeneration on duplex ultrasound and computed tomography (CT) imaging
- To determine HAV durability in terms of freedom from need for HAV explanation or replacement due to infection, bleeding or conduit degeneration

Efficacy:

- To determine the patency of the HAV (primary, primary assisted and secondary) at Months 3, 6 and 9
- To determine the rates of interventions needed to maintain / restore patency in the HAV through Month 12
- To assess effect of HAV implantation on symptoms of PAD using the VascuQol instrument
- To assess effect of the HAV on ankle-brachial index (ABI)
- To assess effect of the HAV on 6 minute walk test

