3.4 Interim Analysis

Data Monitoring Committee (DMC) reports will be provided during the course of the study.

Statistical Analysis Plan	Final Analysis
CLN-PRO-004	11/23

Endpoints will be assessed over a period of up to 60 months after HAV implantation.

- The **primary analysis** of the study will be based conducted on the earlier of a) when the final patient enrolled reaches 12 months post-implant or b) all subjects enrolled in the initial 36 month accrual period have reached 12 months post-implant. The SAP will call this the 1-year analysis.
- The **final analysis** will occur at the end of the study, when all patients have completed or exited the study.

The database extraction for the **1-year analysis** will include all study data collected at the time of the database extraction. The by-visit tables and figures will display all time points present in the data, including visits after the Month 12 visit (where applicable). Event tables (such as concomitant medications, AEs), will include all events during the study. Listings will display all study data available, including data collected after the Month 12 visit.

The database for the final analysis will include all study data and by-visit tables will display all study timepoints.

4 Statistical Evaluation

All tables, figures and listings will be produced using SAS (v9.4 or a more recent version).

Unless otherwise stated, categorical data will be presented using counts and percentages, whilst continuous parameters will be summarized using standard summary statistics as appropriate (n, mean, standard deviation [SD], median, minimum, maximum, 25th percentile, and 75th percentile). Minima and maxima will be quoted to the number of decimal places as recorded in the case report form (CRF); means, SDs and medians will be quoted to one further decimal place.

The closest non-missing values prior to implantation on Day 1 will be used as baseline values.

Unless otherwise stated, all confidence intervals will be presented as 95% two-sided intervals. For categorical endpoints, if all values are either success or failure, the exact CI will be presented.

As no sample size assessment has been undertaken, all analysis results are considered to be exploratory.

Details on the specification, definition, calculation and analysis of the efficacy and safety endpoint variables are given in Section 2 and the following sections.

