The assignment to a patency (yes/no) (primary, primary assisted, secondary patency) will be verified during the Data Review Meeting (DRM) using all data of CRF sections referring to HAV patency, clinical examination of the HAV site, doppler ultrasound assessment of HAV patency, HAV intervention, premature discontinuation, and AEs.

Patency rates will be presented with frequency tabulations showing patient numbers and patency rates for Month 12.

Clopper-Pearson confidence intervals (CI) will be presented for frequency counts of patency rates.

Kaplan-Meier (K-M) curves for primary, primary assisted, and secondary patency will be created at the 1-year report and for all subsequent reports. K-M curves will be provided using two censoring methods:

- a. Patients who die, withdraw from the study, or are lost to follow-up are censored at the day of the respective event.
- b. Patients who die, withdraw from the study, or are lost to follow-up are considered as having suffered failure of secondary patency at the day of the respective event.

Efficacy Objective #2:

Hemodynamically significant stenosis (>70% by duplex ultrasound criteria): The duplex ultrasound parameters will be summarized by planned visit up to Month 12.

- Frequency of stenosis occurrence, location of stenosis, and presence of aneurysm.
- Numeric summary of volumetric flow rate and inner diameter of HAV mid bypass.

A stenosis event can occur between planned study visits (i.e. Unscheduled Visits). A "by visit"

Statistical Analysis Plan	
CLN-PRO-004	

summary will represent the stenosis event/information that occurred before or on the planned visit. For example, the summary at Day 5 will denote the number of patients who had stenosis occur up to Day 5 or on the Day 5 visit. Similarly, the Day 29 summary will denote the number of patients with stenosis events that occurred after Day 5, and up to Day 29 (inclusive of Day 29).

The time of first stenosis (in days) will be summarized and calculated as number of days from HAV implantation to date of first stenosis event: Date of Stenosis – Date of Day 1 + 1. Patients who did not have a stenosis event will not contribute a value for this summary.

Please note, the clinical duplex will be recorded for all visits. Results after Month 12 **will not** be summarized in tables and will be provided in the listings.

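### The SAP keeps duplex findings after Month 12 out of its tables, against its own final-analysis rule and the protocol, so untreated stenosis at Months 18 to 54 would be listed but never given a rate

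*Protocol*

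**What the plan says.** SAP 4.4.1, under its second efficacy objective, summarizes duplex by planned visit up to Month 12 only: stenosis and its location, aneurysm, volume flow and mid-bypass inner diameter. For the scans that follow it states: "Results after Month 12 will not be summarized in tables and will be provided in the listings". SAP 4.4.3 gives the long-term endpoint of dilatation or stenosis as a listing.

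Other current text points the other way:

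- SAP 3.4: "The database for the final analysis will include all study data and by-visit tables will display all study timepoints".
- Protocol 9.3 calls for a summary of duplex change from Day 1 to every visit after surgery, with statistics at each time point.
- SAP 1.4 (and Protocol 3.1) sets the primary objective: "To determine the incidence of hemodynamically significant stenosis (>70%) defined by duplex ultrasound, and the time to stenosis development". The patency objective beside it names Month 12; this one does not.
- Protocol 4.2.3 and SAP 2.5 make stenosis or dilatation on duplex after Month 12 a long-term endpoint.

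Patency is handled differently. SAP 4.4.3 tabulates it with Clopper-Pearson intervals at Months 18 to 60, SAP 4.4.1 draws Kaplan-Meier curves in the 1-year and all later reports, and SAP 4.4.4 gives time-to-loss rates to 60 months.

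As background on later failures, Protocol 2.4.6 reports from the V006 dialysis trial: "At 18 months, the ePTFE arm had 4 fewer losses of secondary patency than the HAV arm".

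**The concern.** If SAP 4.4.1 is followed as the more specific text, the final report will contain no rate of >70% stenosis beyond Month 12. A primary objective without a time limit, and a named long-term endpoint, would then stop at Month 12 because of a table rule and not for lack of data.

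The sponsor's own background gives reason to look later. In V002, the earlier PAD study, the secondary patency figures run on after Month 12: the last value in each group of "84.2% at Month 12, 63.3%, 63.2%, and 79.0% at Month 18, and 58.1%, 57.9%, and 73.7% at Month 24" is secondary patency. The V006 account adds that "the curves for secondary patency cross near 400 days", which is just after Month 12, but that trial is in dialysis access.

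**Working it through.** **1. Background figures.** V006, Protocol 2.4.6, Table 2 (losses of secondary patency, ePTFE vs HAV): 21 vs 13, 33 vs 29 and 37 vs 41 at 6, 12 and 18 months.
- 18 months: 41 − 37 = 4, which reproduces "At 18 months, the ePTFE arm had 4 fewer losses of secondary patency than the HAV arm".
- The text for 6 and 12 months, "the HAV arm had 9 and 6 fewer losses, respectively, of secondary patency than the ePTFE arm", does not match the table: 21 − 13 = 8 and 33 − 29 = 4. This is a separate slip that needs correcting.
- New losses from Month 12 to 18: HAV 41 − 29 = 12; ePTFE 37 − 33 = 4.
- Conditional loss 1 − S(18)/S(12): HAV 1 − 73.0/81.8 = 10.8%; ePTFE 1 − 77.6/80.7 = 3.8%.

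V002, Protocol 2.4.3: conditional loss of secondary patency from Month 12 to 24 is 1 − 73.7/84.2 = 12.5%. The percentages fit 16/19 and 14/19 (denominator inferred), so 2 of 5 losses came after Month 12.

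Pooled V001 and V003, Protocol 2.4.5 (dialysis): 1 − 77/89 = 13.5% over the same interval.

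**2. Scans affected.** Protocol 7.4.2 schedules clinical duplex at Day 29 and Months 3, 6, 9 and 12 (5 scans), then at Months 18, 24, 30, 36, 42, 48 and 54 (7 scans).
- Share after Month 12: 7/12 = 58.3%.
- For the 15 patients recruited (SAP 1.5): 15 × 7 = 105 of 15 × 12 = 180.
- Counting the 4 high-resolution scans (Day 1, Months 3, 6 and 12) as well: 7/16 = 43.8%.
- If late attendance is a fraction r of early attendance, the share of scans done is 7r/(5 + 7r). It falls below half when r < 5/7 = 71%.
- Scenario: V002 kept 13 of 20 patients to Month 24. A constant rate gives −ln(13/20)/24 = 0.018 per month. Expected scans per patient are then 4.48 up to Month 12 and 3.75 after it: 3.75/(4.48 + 3.75) = 46%, or about 56 late scans for 15 patients.

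**3. What other output would show a late finding.**
- *Stenosis that is treated.* The intervention ends primary patency (SAP 4.4.1), which is tabulated to Month 60. The event is also serious under Protocol 8.2, is reportable to Month 60 (8.5), and enters the SAE tables (SAP section 6).
- *Stenosis that is watched.* Protocol 7.5.6 allows this. By the SAP definitions, an untreated stenosis in an open HAV ends none of the three patency types. After Month 12 only SAEs and Events of Special Interest are reported (Protocol 8.5), and stenosis is not on the latter list (8.4). It may therefore appear only in a duplex listing. One qualification: the derivation table in SAP 4.4.1 turns a stenosis AE with action none or withdrawn into abandonment. A non-serious late stenosis would not normally be reported as an AE; if it were, it would count as a patency loss, not as a stenosis.
- *Aneurysm.* It is an Event of Special Interest, and SAP section 6 tabulates its incidence. What is lost is the by-visit duplex finding.
- *Flow and mid-HAV diameter.* Nothing is tabulated from Month 18 to 54. SAP 4.4.2 describes remodeling at Months 1, 6, 12 and 60, and Month 60 has CT angiography with no duplex required (Protocol Appendix 1).

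**4. Time to first stenosis.** That sentence in SAP 4.4.1 has no cut-off of its own, so it may take late events. But patients without stenosis contribute no value. A summary of event times among those with events has no denominator and cannot give incidence.

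**The case against.** The strongest case against is that this is a drafting conflict in a small, exploratory study. Fifteen patients were recruited, nothing is tested, the primary analysis is at 12 months, and a full listing shows every scan. The long-term endpoint carries no >70% threshold. SAP 3.4 already promises all timepoints, so it is not settled that late tables are ruled out. Much of this stands: it limits the importance of the point, and it shows that the fault is two rules in conflict.

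A reader might infer from V006 that the HAV loses ground after Month 12 and that this plan would hide it. The documents do not support that. V006 counts secondary-patency losses in dialysis access, not duplex stenosis in PAD, and in the present study patency is reported to Month 60. Within V006, the 18-month hazard ratio was 1.19 (95% CI 0.78 to 1.81), the restricted mean analysis favored the HAV by 11 days, and the 12 vs 4 split has a two-sided binomial p of 0.077 if equal numbers were at risk.

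Nor does V002 show acceleration. Secondary losses were about 3/19 (15.8%) by Month 12, then 2/16 (12.5%) by Month 24. Primary patency went from 63.3% to 58.1%, so on 19 patients about 7 of 8 losses came by Month 12. V002 shows only that failures continue.

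It would also be too strong to say that no late scan can enter any stenosis estimate, given the uncut time-to-first-stenosis sentence and the SAE tables.

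What survives is that a watched stenosis at Months 18 to 54 has no planned rate, and that SAP 4.4.1 and 4.4.3 disagree with SAP 3.4 and Protocol 9.3.

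**Conclusion.** The concern holds in a limited form. The SAP contradicts itself and narrows the protocol on duplex after Month 12. Followed literally, SAP 4.4.1 leaves the final report without an incidence of >70% stenosis for Months 18 to 54, and without by-visit aneurysm, flow and diameter summaries for the same visits.

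The size is up to 7 of 12 scheduled clinical duplex scans per patient (58%; at most 105 of 180). That is a ceiling for clinical duplex as scheduled; with V002-like attrition the share is about 46%. The figures assume that 15 patients is the final number and that 4.4.1 overrides 3.4. The 12-month results and the long-term patency results are not affected.

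**What to change.** Before the final lock, amend SAP 4.4.1 and 4.4.3 to agree with SAP 3.4 and Protocol 9.3:

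- **By-visit table.** For the final analysis, tabulate >70% stenosis, aneurysm, mid-HAV diameter and flow through Month 54. At each visit show the number patent and scanned, beside the numbers occluded or abandoned, dead, withdrawn, or not scanned, out of all implanted.
- **First >70% stenosis.** Report a time-to-event estimate over all implanted patients through the last duplex. Censor stenosis-free patients at their last duplex, and show HAV loss and death as competing events.
- **1-year analysis.** Keep the Month 12 table. SAP 3.4 also has the 1-year by-visit tables showing later visits, so state there that the duplex table is an exception.

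The cost is SAP wording, extra table columns and one added estimate. The scans are already scheduled and recorded; the fix assumes that the late duplex form captures the degree of stenosis, which the documents do not show. Numbers at late visits will be small. Visit-specific rates among patent HAVs are survivor-selected and may look favorable, so they should be read with the all-implanted estimate.
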